will be the day the first dose of the corresponding COVID-19 vaccination was received. This date in the unexposed group will be a day when an individual did not receive a COVID-19 vaccine dose and randomly chosen by calendar matching to the start date of the corresponding Ad26.COV2.S exposed individual (i.e., a random day during the same week that the matching individual in the exposed cohort receives the Ad26.COV2.S vaccine).

Individuals in the Ad26.COV2.S exposed cohort will be individually matched to one individual in the concurrent unexposed cohort and to one individual in each active comparator cohorts on key clinical variables (exact age, sex, previous COVID-19 infection and presence of one or more risk factors for severe COVID-19 [e.g., cancer, sickle cell disease, obesity, chronic kidney disease, chronic respiratory disease, human immunodeficiency virus infection], and month of vaccination (using calliper if needed)) at the index date.

[figure not shown]
Three sets of matched cohorts of individuals who meet all inclusion and exclusion criteria will be considered as follows:

- Recipients of a first Ad26.COV2.S dose matched to recipients of the first dose of a viral vector COVID-19 vaccine (AstraZeneca vaccine)
- Recipients of a first Ad26.COV2.S dose matched to recipients of the first dose of an mRNA COVID-19 vaccine (Pfizer-BioNTech or Moderna)
- Recipients of a first Ad26.COV2.S dose matched to unvaccinated individuals at the index date (individuals in this cohort may later become eligible to enter the exposed cohorts if vaccinated with a COVID-19 vaccine).

For the matched exposed cohorts, the index date (time zero) will be the date of the corresponding COVID-19 vaccine. For the unvaccinated individuals, the index date will be assigned as the index date of the matched exposed individual (see [Figure 2](#)). Additional details regarding matching will be included in the SAP.

Follow-up for unexposed persons is censored when the individual receives a COVID-19 vaccine. In a sensitivity analysis, vaccination with other non-COVID-19 vaccines will also be an exclusion and censoring event.

Figure 2: Schematic Overview of the Cohort Study Design

AESI = adverse event of special interest; COVID-19 = coronavirus disease 2019; FU = follow-up; SARS-CoV-2 = severe acute respiratory syndrome coronavirus-2.

Note: In the figure 1 year enrolment refers to the inclusion criterion to have at least 12 months of data available before the index date.

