8.2.2. Source Population

The source population will be made up of all individuals registered in each of the participating health care data sources.

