8.2.3. Study Duration and Follow-Up

Feasibility Assessment

For the feasibility assessment, the study period will start on the date when each participating country begins with the Ad26.COV2.S vaccine or the latest date when the individual is registered in the data source (plus 365 days) or born and will end a maximum of 12 months thereafter. Individuals will be followed until the earliest of the following dates: death, end of data availability, individual exit from the data source, or the completion of the period.

Safety Evaluation Study

- For the SCRI design, the study period will start at the date of the start of the pre-vaccination control window (Table 1). Follow-up ends at the earliest of the following: death, end of data availability, individual withdrawal of the study, end of the post-vaccination risk or control window, or receipt of another COVID-19 vaccine. In a sensitivity analysis, follow-up will be censored upon receipt of other vaccines (non-COVID-19 vaccine). We will also compare the Ad26.COV2.S vaccine with active comparators with 1) only 1-dose strategy and 2) a 2-dose strategy. Figure 1 shows the different periods considered for the SCRI design.
- For the cohort design, the study period will start at the date when each participating country will begin with the Ad26.COV2.S vaccine and will end at the end of data availability at each data source. For the cohort design, the follow-up will start at the beginning of the vaccination risk window, as detailed in Table 1 and ends at the occurrence of each AESI, death, end of data availability, individual exits the database, after one year of follow-up, receipt of a

COVID-19 vaccine (unexposed cohort only), receipt of a different COVID-19 vaccine from the one granting access to the study (exposed cohorts only). For the vaccine-exposed comparator groups, a second dose of the same corresponding vaccine will be allowed (more details will be provided in the SAP). In a sensitivity analysis, follow-up in the cohort study will be censored upon receipt of other vaccines (non-COVID-19 vaccine). Another sensitivity analysis will also compare the Ad26.COV2.S with active comparators with (1) a 1-dose strategy and (2) a 2-dose strategy. For the subgroup analysis of subjects without COVID-19 at the start of risk window, patients will be censored if they develop COVID-19 during follow-up.

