8.2.4.3. Cohort Design

Individuals must meet all the following inclusion criteria to be eligible for inclusion in the cohort study:

- Have received their first-ever dose of the corresponding COVID-19 vaccine within the study period
- Had at least 12 months of data available before the index date or were born in the previous 12 months and have been enrolled since birth

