Health Care Utilisation in the Year Before and in the 4 Weeks Prior to Index Date

- Number of individuals with at least one hospitalisation (hospitalisation data sources)
- Number of individuals with at least one GP-visit (Primary care data sources)
- Number of different dispensed/prescribed drugs ATC Level 5 dispensed (all data sources)

The AESI may have different sets of risk factors, and outcome-specific analyses may contain different covariate sets. Potential covariates may include the following information, as available in each data source. For the SCRI design, covariate status will be measured at start of risk window and control window for time-varying factors.

For the secondary analyses in subgroups, the following categories will be used:

- Immunocompromised individuals,
- Pregnant women,
- Prior COVID-19 infection,
- Individuals who have a prior history of thrombotic events or thrombocytopenia,
- Individuals with a prior history (ever) of that event (i.e., more than a year before).

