dedicated systems have been set up to track COVID-19 vaccine administration, in others it is fragmented between primary care and other places. Linkable COVID-19 vaccine registers are in place for Norway, ARS, SIDIAP and FISABIO. For PHARMO information on COVID-19 vaccination is not collected comprehensively in the primary care records, especially not for those vaccines that were administered early and targeted at the frail population. For the SCRI design and acute events, this is not of concern for internal validity, as it will include only individuals vaccinated with the Ad26.COV2.S vaccine. For the non-acute design with non-exposed comparators, misclassification may occur in the non-exposed cohort, which might have been vaccinated with another COVID-19 vaccine. Matching on age will reduce this risk as most of the roll-out strategies were age-based, but still, healthcare workers or other professional groups, which were eligible for early vaccination may be erroneously classified as non-exposed. This would lead to an attenuation of the risk of AESI if it would be associated with the AESI. We will conduct a sensitivity analysis that will exclude non-exposed comparators in databases with misclassification for non-COVID-19 vaccinated

Misclassification of risk window

Experience with other vaccines indicates that safety risks may occur within specific periods post-vaccination, for example, the risk of Guillain-Barré syndrome within 6 weeks after the swine flu vaccine. However, for most of the AESIs included in this study, the risk windows following Ad26.COV2.S vaccines are not clearly established; theoretical risk windows based on previous experience, mechanistic evidence and biological plausibility are considered. For this reason, a subset of the listed AESIs (to be defined in the SAP) will also be assessed within a larger risk window in sensitivity analyses.

For non-acute events, the primary study design will be the cohort design with concurrent matched unexposed comparators. The advantage is that misclassification errors will be reduced because of misspecification of the risk window that may happen in the SCRI, but at the same time, person-time at risk because of the larger time windows may be diluted, which would dilute a potential increased risk.

Confounding

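### In the cohort contrast with unexposed people, 12 months of enrolment is the only proof of presence, so registrants who are absent without a recorded exit would bias the rate ratio upwards by an unknown amount

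*Protocol*

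**What the plan says.** Section 8.2.2 sets the base population by registration: "The source population will be made up of all individuals registered in each of the participating health care data sources". Section 8.2.4.3 then gives two inclusion criteria for the cohort design.

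- The first is "Have received their first-ever dose of the corresponding COVID-19 vaccine within the study period". An unexposed person cannot meet it, so it can only apply to the vaccinated cohorts.
- The second is "Had at least 12 months of data available before the index date or were born in the previous 12 months". The note to Figure 2 (Section 8.1.2.2) explains it: "In the figure 1 year enrolment refers to the inclusion criterion to have at least 12 months of data available before the index date".

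The exclusions in Section 8.2.5 concern earlier COVID-19 vaccination and the AESI during its washout. The matching list in Section 8.7.2.1 covers age, sex, pregnancy, immune status, prior COVID-19, calendar time and risk factors. Neither asks for any contact with health care.

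Under Section 8.2.3, cohort follow-up "ends at the occurrence of each AESI, death, end of data availability, individual exits the database, after one year of follow-up". Section 8.1.2.2 adds: "Follow-up for unexposed persons is censored when the individual receives a COVID-19 vaccine". Section 8.7.1.2 defines the rate as cases over person-time. Section 8.9 states: "For non-acute events, the primary study design will be the cohort design with concurrent matched unexposed comparators".

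Prior health care use is collected. Section 8.3.4 lists admissions, drug counts and "Number of individuals with at least one GP-visit (Primary care data sources", in the year and in the 4 weeks before index. Section 8.7.1.2 plans standardised differences, and then covariate or propensity-score adjustment where imbalance is found.

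**The concern.** The presence test differs between the arms. A vaccinee is shown to be present and in contact with the system by the dose itself. An unexposed comparator need only be enrolled. Someone who has moved away without a recorded exit, or who receives all care elsewhere, still qualifies. That person can have no recorded AESI and no recorded vaccination, so follow-up runs to one year or to the end of data.

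Censoring at vaccination makes this worse, because it shortens follow-up only for comparators who are present. Absent people therefore hold a larger share of unexposed person-time than of unexposed persons. The unexposed rate falls, and the rate ratio and attributable risk rise. The affected comparison is part of the primary analysis for autoimmune thyroiditis, multiple sclerosis, acute aseptic arthritis and type 1 diabetes, and it also serves as a sensitivity analysis for the acute AESIs.

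Section 8.9 describes error in the unexposed group only as missed vaccination, with attenuation as the result. A reader would not look for a bias in the other direction.

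**Working it through.** **The plan's own figure.** The protocol gives no figure for this bias. The nearest one is the cohort size in Table 2. Events per arm: A = 2 × [(1.960 + 0.842) / ln 3]² = 13.0. Subjects: N = A / (0.001 × 60/365) = 79,121. This matches Table 2 for an upper limit of 3 at 100 per 100,000 person-years, and the other 15 cells agree to within one subject.

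**Inputs for the bias (assumptions, not in the protocol).** g is the share of the unexposed cohort that is absent at index. m is the mean number of years a genuine comparator contributes before censoring. Absent people contribute one year and no events.

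**Formula.** Unexposed person-time per head is (1−g)m + g, and only (1−g)m can yield events. Observed IRR / true IRR = 1 + g / [(1−g)m].

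| g | m = 1 | m = 0.5 | m = 0.25 | m = 0.1 |
|---|---|---|---|---|
| 1% | 1.01 | 1.02 | 1.04 | 1.10 |
| 2% | 1.02 | 1.04 | 1.08 | 1.20 |
| 5% | 1.05 | 1.11 | 1.21 | 1.53 |
| 10% | 1.11 | 1.22 | 1.44 | 2.11 |

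The factor exceeds 1 for every g above 0, so the direction does not depend on the assumed values.

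**Exponential time to vaccination.** With a mean of 60 days, genuine follow-up averages 60 × (1 − e^(−365/60)) = 59.9 days. For g = 5%, absent people hold 18.25 / (18.25 + 0.95 × 59.9) = 24% of person-time, and the factor is 1/(1 − 0.243) = 1.32. With a mean of 120 days it is 1.17. For g = 2% and 60 days it is 1.12. For g = 1% and 120 days it is 1.03.

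**Concentration in the unvaccinated pool.** If a share q of registrants is absent and coverage among those present is c, then g = q / [q + (1−q)(1−c)]. With q = 2%, g is 3.9% at 50% coverage, 7.5% at 75% and 16.9% at 90%. This ignores matching.

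**Consequences when the true IRR is 1.**
- Attributable risk: at 100 per 100,000 person-years and a factor of 1.21, the spurious difference is 100 − 100/1.21 = 17 per 100,000 person-years.
- Table 2 example (60-day window, no early censoring): the chance of an upper limit below 3 falls from 80.0% to 78.1% (g = 2%), 75.1% (5%) or 69.3% (10%).
- The minimum target of 100,000 exposed, followed for one year at the same rate, with g = 5% and m = 0.25: expected events are 100 and 23.75, the SE of the log ratio is √(1/100 + 1/23.75) = 0.228, and the chance that the lower limit exceeds 1 is 13% instead of 2.5%.

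**What adjustment does.** Suppose a share u of genuine people had no GP visit in the prior year, with event rate r relative to visitors. Absent people all fall in the no-visit stratum, where the observed unexposed rate is (1−g)um·r / [(1−g)um + g]. Standardising to the exposed mix with g = 5%, m = 0.25, u = 10-25% and r = 0.3-1.0 (all assumed) brings 1.21 down to between 1.02 and 1.13.

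**The case against.** The strongest reply is that the plan already holds much of the remedy. Absent registrants score zero on admissions, GP visits and drug counts, so the problem should show up in the standardised differences of Section 8.7.1.2 and lead to adjustment. That stands in part: the factors in the table are unadjusted, and adjustment could remove most of the excess. But it depends on the imbalance found and on association with the outcome, and it leaves a remainder because absent people stay mixed with healthy non-users.

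Follow-up also ends at a recorded exit, and Section 8.4.2 says that VID's population register holds discharge and death dates. That protects where exits are recorded. It is also why a reader should not infer that the bias is largest in the most registry-like sources. The protocol does not support that, and VID points the other way.

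Matching on pregnancy, immune status, prior infection and risk factors makes some exposed people hard to pair with someone who has no recent records. This limit is real but partial.

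A reader might also infer that a false safety signal is to be expected. The protocol does not support that either. It gives neither g nor m. The two active-comparator contrasts and the SCRI are not affected by this route. Table 5 plans negative-control data, which might reveal the bias, and Section 8.9 acknowledges residual confounding in general and describes quantitative bias analysis. Unrecorded vaccination in PHARMO's unexposed group would attenuate a true risk, so the net direction of the pooled estimate is not established.

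Finally, requiring contact for primary eligibility is a debatable trade. Sources record different kinds of contact, and healthy non-users would be lost.

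**Conclusion.** The point holds as a directional bias of unknown size, confined to the cohort contrast with unexposed people. Enrolment is the only presence test for that group, and any registrant absent without a recorded exit lowers its rate. Before adjustment the rate ratio is multiplied by about 1.01-1.04 if 1-2% are absent and genuine comparators stay at least half a year on average. It is multiplied by about 1.2-1.3 if 5% are absent and genuine comparators are vaccinated within about two to three months. All of these shares and times are assumptions. Conditional adjustment and censoring at recorded exit reduce the bias without removing it. The planned sensitivity analysis that drops sources with poor vaccine capture addresses missed vaccinations, which is a different error. This justifies a cheap added analysis. It does not show that the primary eligibility criteria must change.

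**What to change.** - Add to Section 8.7.6 a sensitivity analysis of the unexposed contrast restricted, in both cohorts, to people with at least one recorded health care contact in the 12 months before the index date. Contact means a visit, an admission or a prescription/dispensing, as available in each source, and does not include COVID-19 vaccination.
- State in Section 8.7.1.2 that prior-year health care use is always in the adjustment set for this contrast, whether or not imbalance is found.
- Name the upward bias in Section 8.9 beside the attenuation already described.

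The variables are already listed in Section 8.3.4, so the cost is one more run and a few lines of text. The restricted analysis loses some healthy non-users, and its definition of contact will vary by source, so the definition used should be reported for each source. People who left after a contact within the look-back year would remain, so the restriction brings the factor close to 1 but does not guarantee it.

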8.2.5. Exclusion Criteria

For the feasibility assessment, there will be no exclusion criteria.

Individuals will be excluded from the safety evaluation study if:

- They have been vaccinated with any other COVID-19 vaccines before starting each risk window.

- Record of the specific AESI during the specific corresponding washout periods for the SCRI and cohort analyses. Individuals with such acute diagnoses before the AESI-specific washout periods will not be excluded. For clarification, when one AESI will be investigated, any history or prevalence of other AESIs will not be excluded. [Table 1](#) shows the specific washout periods for each AESI.

8.3. Variables

8.3.1. Exposure Assessment

Exposure will be based on available prescriptions, dispensing, or administration of the Ad26.COVS.S and other COVID-19 vaccines. Vaccine receipt and date of vaccination will be obtained from all possible sources that capture COVID-19 vaccination, such as pharmacy dispensing records, general practice records, immunisation registers, vaccination records, medical records, or other data banks. During the feasibility assessment, the completeness of information will be assessed and described. Depending on the data source, vaccines may be identified via nationally used product codes (including batch numbers) where possible. The exposure of interest for the safety evaluation study is the receipt of Ad26.COVS.S vaccine.

- SIDIAP (ES): SIDIAP will have available information on the administration of COVID-19 vaccines to individuals linked to a unique and anonymous identifier. The information will be originated from the electronic medical records. For each patient, SIDIAP will have the date and centre of administration, health professional administering the vaccine, dose, brand, reasons for vaccination (e.g., risk group), and other information related to vaccination.
- VID (ES): For the inhabitants of the Valencia region, FISABIO will capture all COVID-19 vaccines through the immunisation register. The Vaccine Information System includes administration dates, brand and batch from each dose.
- PHARMO DATABASE NETWORK (NL): Data on vaccination will be obtained from PHARMO's general practitioners' GP database. Information on vaccines includes brand, batch, and date of administration/recording. Several COVID-19 vaccines have been administered outside traditional medical care settings and linkage with a GP database is not yet implemented, this may change over time.
- ARS Toscana (IT): ARS will identify vaccines from the regional immunisation register using the nationally used product code, including batch number. See section [8.2.1](#) regarding conditional participation of ARS Toscana.

The vaccination strategies for the different exposure groups will be defined as follows:

- Individuals who receive the first dose of the Ad26.COVS.S vaccine will be classified as exposed to Ad26.COVS.S vaccine. Individuals will be censored if and when they receive a non-Ad26.COVS.S COVID-19 vaccine during follow-up. Individuals who receive a second dose of Ad26.COVS.S vaccine will also be censored at the date of that dose as this is not the current dosing schedule. When the dosing schedule changes for Ad26.COVS.S vaccine, the study protocol may be amended.

- The vaccination strategy for the matched unexposed group will be defined as not receiving a COVID-19 vaccine of any brand during the follow-up period. Individuals will be censored when they receive a dose of any COVID-19 vaccine during the observation period.
- The vaccination strategy for the matched groups receiving other COVID-19 vaccines will be defined as 1) receiving a viral vector COVID-19 vaccine (i.e., Vaxzevria[®] [AZD1222] by Oxford/AstraZeneca) or 2) receiving a mRNA COVID-19 vaccine (i.e., Comirnaty[®] [tozinameran] by Pfizer/BioNTech or Spikevax[®] [elasomeran] by Moderna). Individuals will be censored when they receive a dose of a COVID-19 vaccine of a different type during the observation period (e.g., a patient with the first dose of AZD1222 receives a second dose with a mRNA COVID-19 vaccine).

For the SCRI design, person-time in the risk interval will be considered “exposed” while person-time in the control interval will be considered “unexposed.” Risk intervals are specific to the outcome of interest.

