A general description of the planned statistical methods to be used to analyse the data collected in this study is presented in the main body of the document. Additional details will be provided in the SAP.

For the feasibility analysis, the utilisation patterns of Ad26.COV2.S and other COVID-19 vaccines will be characterised and monitored over time. Description of demographics and clinical characteristics will be reported overall and for different groups of vaccine recipients.

The primary analysis of non-acute AESIs will focus on calculating and comparing the incidence rates between individuals exposed to Ad26.COV2.S and:

1. unexposed individuals
2. individuals exposed to another viral vector COVID-19 vaccine (i.e., Vaxzevria® [AZD1222] by Oxford/AstraZeneca); and
3. individuals exposed receiving a mRNA COVID-19 vaccine (cohort).

For acute events, the relative risk between risk window and control window will be estimated (SCRI) among individuals exposed to Ad26.COV2.S.

All analyses will be conducted within each data source and pooled across data sources using a random-effects model.

For the COVID-19 vaccines with a 2-dose schedule, AESI-specific risk windows after each dose of the comparator will be considered for the cohort analyses.

Analyses within the primary study designs (cohort design for non-acute events and SCRI design for acute events) will be stratified by the clinically relevant subgroups below. Stratification will be done also for matching variables when considered relevant.

- Selected comorbidities, including risk factors for severe COVID-19 (by presence or absence of each comorbidity)
- Frailty score (categorized)

-
- Age (0-17, 18-29, 30-39, 40-49, 50-59, 60-69, 70-79, 80+ years)
 - Sex.

Sensitivity analyses will be performed to:

- Assess the risk of AESI within extended disease-specific risk windows for events for which the risk interval is not well known or documented in the vaccine safety literature.
- Assess the impact of data sources that are shown not to capture vaccinations well during the feasibility assessment. In the sensitivity analyses with non-exposed comparators those data sources from the cohort analysis for the acute and non-acute events will be excluded, to avoid misclassification of exposure.
- Address the different dosing schedules between Ad26.COV2.S and the comparator vaccines used in the analyses, comparing the Ad26.COV2.S vaccine with active comparators with (1) a 1-dose strategy and (2) a 2-dose strategy.

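### Section 8.3.1 ends Ad26.COV2.S follow-up at any further COVID-19 dose but comparator follow-up only at a different vaccine type, and Section 8.2.3 does not settle what a third same-vaccine dose does

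*Protocol*

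**What the plan says.** Protocol Section 8.3.1 sets the censoring triggers by exposure group.

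- **Ad26.COV2.S, other vaccine:** "Individuals will be censored if and when they receive a non-Ad26.COVS.S COVID-19 vaccine during follow-up".
- **Ad26.COV2.S, second dose:** a recipient of a second dose of the "vaccine will also be censored at the date of that dose as this is not the current dosing schedule".
- **Active comparators (Vaxzevria; mRNA):** "Individuals will be censored when they receive a dose of a COVID-19 vaccine of a different type during the observation period". The example given is a first Vaxzevria dose followed by an mRNA dose.

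Section 8.2.3, repeated in the abstract, describes the end of cohort follow-up differently. For the vaccinated cohorts the vaccine trigger is "receipt of a different COVID-19 vaccine from the one granting access to the study (exposed cohorts only", and for the comparators "a second dose of the same corresponding vaccine will be allowed", with more detail promised in the SAP.

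The abstract treats the comparators as two-dose vaccines: "For the COVID-19 vaccines with a 2-dose schedule, AESI-specific risk windows after each dose of the comparator will be considered". Section 8.7.1 repeats this and leaves further detail on different doses to the SAP. The vaccination list in Section 8.3.4 names receipt of another COVID-19 vaccine as the censoring criterion. Non-acute events are counted over days 1–365 (Section 7; Table 1).

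**The concern.** For Ad26.COV2.S, Section 8.3.1 applies a clear principle: follow-up stops at a dose outside the schedule under study, whatever the brand. The comparators have no matching rule. An mRNA recipient who gets a third mRNA dose never meets the different-type trigger.

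Section 8.7.1 lists Ad26.COV2.S versus mRNA among the three comparisons in the primary analysis of non-acute events. Under 8.3.1 that comparison could set time after one Ad26.COV2.S dose against time after an mRNA primary series plus a booster. If a booster raises the rate of an event, the comparator rate rises and the rate ratio falls, which in a safety study can hide an excess. The two arms would also cover different parts of the year.

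The comparison with unexposed individuals is not affected, because they are censored at any COVID-19 vaccine. Acute events are little affected, since their risk windows are at most 60 days.

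**Working it through.** **1. The rules side by side.**

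| Event during follow-up | Section 8.3.1 | Section 8.2.3 and abstract |
|---|---|---|
| Ad26.COV2.S recipient, non-Ad26 vaccine | censored | censored |
| Ad26.COV2.S recipient, second Ad26.COV2.S dose | censored | not censored by the stated trigger |
| Comparator, second dose of same vaccine | not censored | allowed |
| Comparator, third dose of same vaccine | not censored | not stated |
| mRNA recipient, switch to the other mRNA brand | not censored (same type) | censored if a different vaccine means a different brand |
| Vaxzevria recipient, mRNA dose | censored | censored |

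Two points follow. Under 8.3.1 the arms of the mRNA comparison follow different rules for a dose beyond schedule. The two sections also disagree on the second Ad26.COV2.S dose and, on a brand reading, on switches between mRNA brands. In addition, an mRNA booster ends follow-up in the Vaxzevria cohort but not in the mRNA cohort, so under 8.3.1 the two active comparisons treat it differently.

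**2. Whether the model repairs it.** The Poisson model in Section 8.7.1.2 has an exposure term and a log person-time offset. Calendar time is matched at the index date, and adjustment is for baseline imbalance. No term is stated for time since vaccination or for receipt of a booster. With a constant rate and no booster effect, unequal follow-up costs precision but does not bias the ratio. If the rate varies over the year, or a booster changes it, the ratio is biased.

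**3. Illustration.** The plan states no figure to reproduce, and the documents give no booster uptake, timing or effect. All inputs here are assumptions: a proportion u of each arm receives a further dose at day t, every comparator booster is of the same type, and the event rate after it is r times the earlier rate until day 365. Death and database exit are ignored.

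- Post-booster share of comparator time: s = u(365 − t)/365
- Mean Ad26.COV2.S follow-up: (1 − u)·365 + u·t days, against 365
- Factor applied to the rate ratio: 1/[1 + s(r − 1)]

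| u | t | s | Ad26.COV2.S mean days | factor, r = 1.5 | factor, r = 2 |
|---|---|---|---|---|---|
| 0.3 | 270 | 28.5/365 = 0.078 | 336.5 | 0.96 | 0.93 |
| 0.4 | 240 | 50/365 = 0.137 | 315 | 0.94 | 0.88 |
| 0.5 | 180 | 92.5/365 = 0.253 | 272.5 | 0.89 | 0.80 |
| 0.7 | 150 | 150.5/365 = 0.412 | 214.5 | 0.83 | 0.71 |
| 0.8 | 150 | 172/365 = 0.471 | 193 | 0.81 | 0.68 |

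For example, with u = 0.7, t = 150 and r = 1.5, the factor is 1/(1 + 0.412 × 0.5) = 0.83. A true ratio of 1 would read 0.83. Across the whole table a true ratio of 1.5 would read between 1.44 (first row, r = 1.5) and 1.02 (last row, r = 2). With r = 1 and a constant rate the factor is 1.

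**The case against.** **Dose handling is left to the SAP.** Sections 8.2.3 and 8.7.1 do promise detail there, and a third-dose date could be among it. But 8.3.1 already fixes the triggers and fixes them unequally. Section 8.7 also requires a protocol amendment for any major change to the analysis of primary endpoints.

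**Section 8.2.3 may exclude a third dose.** Naming only a second dose as allowed can be read as not allowing a third. This stands as a fair reading. A reader might infer that every section follows comparators through a booster; the text does not support that, and 8.2.3 is best called unresolved. Equally, nothing there ends follow-up at a third dose.

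**The asymmetry is not the same throughout.** This also stands. On the 8.2.3 wording a second Ad26.COV2.S dose ends nothing, so both arms share the different-vaccine trigger and much of the imbalance disappears. The firm statement concerns 8.3.1.

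**A planned analysis addresses dosing.** Section 8.7.6 and Table 5 compare Ad26.COV2.S with comparators under one-dose and two-dose strategies. The two-dose version might drop third-dose time, but no such rule is stated and it is a sensitivity analysis.

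**The comparison carries less weight.** Section 8.1.2 makes the concurrent unexposed group the primary comparator and adds the active groups where possible, while Section 8.7.1 lists all three in the primary analysis. The point is confined to the active comparisons.

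**Conclusion.** The point holds in limited form. Section 8.3.1 gives Ad26.COV2.S recipients and active comparators different rules for a dose beyond schedule, and Section 8.2.3 and the abstract neither repair this nor agree with 8.3.1 on a second Ad26.COV2.S dose. Followed as written, 8.3.1 keeps mRNA time after a third dose in a one-year comparison that Section 8.7.1 lists as primary.

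A reader might infer that the rate ratio is certainly biased downwards, or by a known amount. The documents do not support that. Bias requires a booster effect on the event or a rate that varies over the year. The direction towards hiding an Ad26.COV2.S excess applies if boosters raise the rate; seasonal or other variation could act either way. The factors of 0.68–0.96 are illustrations on assumed uptake, timing and effect. They lie on the high side, because they treat every comparator booster as same-type and uncensored and ignore other losses to follow-up. Shorter Ad26.COV2.S follow-up is not in itself a bias.

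**What to change.** Reconcile Section 8.2.3, the abstract and Section 8.3.1 so that one analysis rule covers all vaccinated cohorts: follow-up ends at the first COVID-19 vaccine dose, whatever the brand, beyond the index vaccine's primary schedule as the protocol defines it (one dose for Ad26.COV2.S, two for the comparators). This extends to the comparators the principle that 8.3.1 already states for Ad26.COV2.S. It governs person-time only and implies no view on vaccination schedules. Align the criterion in Section 8.3.4 with it, and keep the version without this comparator censoring as a sensitivity analysis so that the effect of the rule can be seen.

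The cost is a sentence in each place and one programmed censoring date, since Section 8.3.1 already obtains vaccination dates. The downside is less late comparator person-time, and so some loss of precision in the active comparisons.
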